The proposed study will use the DERRI to identify diabetic patients at high-risk of readmission who will be provided with a novel intervention designed to reduce hospital utilization rates within 30 days of discharge. This multifactorial intervention builds on techniques effectively used in other inpatient populations, specifically, patient-centered discharge education, peri-discharge coordination of care, and post-discharge support by nurses and community health workers (CHWs), and adapts them to patients with diabetes.[2-8] In addition, the intervention includes adjustment of diabetes therapy upon discharge based on the admission A1c, which improves post-discharge glycemic control and is associated with a lower risk of 30d readmission.[9, 10]

Readmission Pilot Trial

We propose a pilot randomized controlled trial to address the following aims:

Aim 1: To explore the feasibility, acceptability, and efficacy of a novel multifactorial intervention designed to reduce all-cause readmission or ED visit rates within 30 days of discharge among hospitalized patients with diabetes who are identified as high risk based on the DERRI

Aim 2: To prospectively validate the readmission risk predictions generated by the DERRI

The usual care control group will provide the baseline risk of 30d post-discharge hospital utilization in the patient population predicted to be at high risk by the DERRI. Furthermore, we will prospectively follow patients who are predicted to be at lower risk to validate the DERRI in this population.

5) Background

Significance

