The **low-risk group** will be followed in a prospective, observational arm of the study. About 5 weeks after hospital discharge, the Temple medical record will be reviewed for the presence of any hospital or ED visits within 30 days after discharge. If no post-discharge acute visits are found, then the subject will be contacted to determine if any hospital or ED visits occurred at another institution.

- The following data will be collected at baseline: sociodemographics, medical history, including HIV, substance abuse, and mental health status, which are likely risk factors for admission, relevant laboratory results, admission diagnoses, well-being (WHO-5), diabetes-related distress (PAID scale), perceived social support (MSPSS), perceived stress (PSS), diabetes knowledge (DKT2), depression screening by the 2-item Patient Health Questionnaire (PHQ-2), [48] and health literacy by the Brief Health Literacy Scale (BHLS). [49, 50] Subjects who score 3 or more on the PHQ-2 will complete the PHQ-9. [51] Subjects with a PHQ-9 score of 5 or more will be referred to their primary care physician (PCP) for evaluation and management of possible depression. [52] For subjects without a PCP, a study physician will begin medical therapy for depression as needed. For subjects newly discovered to be suicidal, psychiatry will be consulted in the hospital.
- The following data will be collected during follow-up: A1c, discharge diagnoses, hospital readmission (date, primary diagnosis), ED visits (date, primary diagnosis) and patient experience according to a brief questionnaire (Appendix Item 3a).

High-risk group:

For the **high-risk group**, there are two phases in the protocol. Phase A is the pilot RCT to explore the feasibility, acceptability, and efficacy of the intervention. Phase B consists of in-depth interviews with intervention participants and research staff to further explore acceptability and effects of the intervention and to refine the protocol for future study. Subjects in the high-risk group will be randomly assigned with a computer-generated randomization scheme 1:1 in randomly permuted blocks of 2, 4, or 6 to receive either the intervention, the Diabetes Transition of Hospital Care (DiaTOHC) Program (“My Temple Extra Care Service”) or usual care (control).

Phase A: RCT of readmission risk reduction intervention

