Adverse events								X
Low-risk group								
Chart review/phone call								X
Psychometric assessments	X							X
Diabetes knowledge	X							X
A1C	X							X
30d endpoints								X

Readmission Pilot Trial

of follow-up appointments, confirming access to medications, and answering questions.

Data collection: The following data will be collected at baseline: A1c, sociodemographics, medical history, including HIV, substance abuse, and mental health status, which are likely risk factors for admission, relevant laboratory results, admission diagnoses, self-reported goals for health and diabetes, well-being (WHO-5), diabetes-related distress (PAID scale), perceived social support (MSPSS), perceived stress (PSS), diabetes knowledge (DKT2), depression screening by the PHQ-2/9, and health literacy by the BHLS (Table 2).

The following data will be collected during follow-up: A1c, discharge diagnoses, hospital readmission (date, primary diagnosis), ED visits (date, primary diagnosis), physician follow-up appointments scheduled and/or attended, post-discharge medication reconciliation (yes/no), cost of post-discharge care, self-monitored blood glucose levels, Nurse Navigator time to deliver the intervention (minutes), well-being (WHO-5), diabetes-related distress (PAID scale), perceived social support (MSPSS), perceived stress (PSS), diabetes knowledge (DKT2), depression (PHQ), and patient experience according to a brief questionnaire (**Appendix Item 3a [usual care] or 3b [intervention]**). These follow-up data will be collected during a phone call about 5 weeks after the index discharge. Baseline and 3-month post-discharge A1c levels will be obtained as part of standard-of-care. A letter reminding patients to do the 3-month blood draw for the A1c test will be sent by mail.

Data will be collected by phone interviews with subjects and review of the electronic medical record (EMR). The Research Specialist will be primarily responsible for screening and recruiting subjects, data collection and data entry.

Phase B: Qualitative evaluation of intervention

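### Low-risk subjects with only a Temple ED visit need not be asked about a readmission elsewhere; taken alone, this can only lower the low-risk readmission rate used in Aim 2 (minor)

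*Protocol*

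**What the plan says.** **Low-risk ascertainment (Protocol, section 8(f), Low-risk group).** About 5 weeks after discharge the Temple record is searched for any hospital or ED visit in the first 30 days. The next step is conditional: "If no post-discharge acute visits are found, then the subject will be contacted", and the purpose is "to determine if any hospital or ED visits occurred at another institution". The condition pools the two kinds of visit, so either one at Temple removes the trigger.

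**Other low-risk follow-up.** The same section lists readmission and ED visits, each with date and primary diagnosis, as follow-up data without limiting them to Temple. It also lists a short experience questionnaire (Appendix Item 3a). Table 2 gives this group a chart review or phone call, repeat psychometric and diabetes knowledge assessments, and the 30-day endpoints.

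**Use of the data (section 4).** Aim 2 is "To prospectively validate the readmission risk predictions generated by the DERRI". For that purpose, "we will prospectively follow patients who are predicted to be at lower risk to validate the DERRI in this population". For the high-risk stratum, "The usual care control group will provide the baseline risk of 30d post-discharge hospital utilization".

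**Endpoints (section 8(e)).** Readmission is the primary outcome. ED visits are a separate secondary outcome, and a composite of the two is a third.

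**High-risk groups (section 8(f), Phase A, Data collection).** "These follow-up data will be collected during a phone call about 5 weeks after the index discharge". Phone interviews and review of the electronic record are the stated sources. The call does not depend on what the record shows, but no question about other institutions is stated.

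**The concern.** Stopping at the first Temple acute visit suits a yes/no composite of readmission or ED visit, because any such visit settles that outcome. It does not suit readmission alone. A subject seen in the Temple ED and later admitted to another hospital has the event that the DERRI predicts, yet the stated rule does not require anyone to find it.

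What is at stake is Aim 2. If outside readmissions are not sought in these subjects, the observed low-risk rate is too low, and the agreement between predicted and observed risk is misjudged. Low-risk ED visit counts can also be too low, because visits elsewhere need not be asked about once Temple shows any acute visit. Analysis cannot recover an event that was never asked about, so the remedy belongs in the data collection procedure.

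**Working it through.** The protocol gives no readmission rate or precision for the low-risk group, so there is no planned figure to reproduce.

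**Direction.** Classify each low-risk subject by four yes/no facts: Temple readmission, Temple ED visit, outside readmission, reachable by phone. That gives 16 combinations. Compare the written rule with a rule that asks everyone who has no Temple readmission. Assume that a subject who is not asked is coded as not readmitted.

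- Temple readmission: already an event under both rules.
- No Temple visit of either kind: asked under both rules.
- Temple ED visit only, reachable, readmitted elsewhere: non-event under the written rule, event if asked.
- Temple ED visit only, reachable, not readmitted elsewhere: non-event under both.
- Temple ED visit only, unreachable: the written rule keeps the subject in the denominator as a non-event. If asking were required, the subject would be missing or, if missing is coded as none, identical under both rules.

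No combination raises the rate under the written rule. Where the rules differ, the rate falls, or stays at zero if there are no events.

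**Size.** The group size of 180 is from section 8(c), where it is part of a ceiling of 300. Everything else is assumed: *e*, the share with only a Temple ED visit, 5–15%; *r*, the share of those readmitted elsewhere, 5–10%; all subjects reachable. Missed readmissions = 180 × *e* × *r*.

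| *e* | *r* | Missed of 180 | Percentage points |
|---|---|---|---|
| 5% | 5% | 0.45 | 0.25 |
| 10% | 7.5% (midpoints) | 1.35 | 0.75 |
| 15% | 10% | 2.7 | 1.5 |

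**Against sampling error.** At an assumed true low-risk rate of 12% (180 × 0.12 = 21.6 events), the 95% half-width is 1.96 × √(0.12 × 0.88 / 180) = 0.0475, about 4.7 points.

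**Calibration.** If the mean predicted risk is also 12%, observed/expected at the midpoints is (21.6 − 1.35)/21.6 = 20.25/21.6 = 0.94 instead of 1.00. Over the range it runs from 21.15/21.6 = 0.98 to 18.9/21.6 = 0.88.

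**High- versus low-risk contrast.** Assume a true usual-care rate of 25%, so that the true ratio is 25/12 = 2.08. At the midpoints the observed low-risk rate is 20.25/180 = 11.25%.

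- Usual care captures every outside readmission: 25/11.25 = 2.22, too high.
- Usual care misses 20% of its readmissions (assumed): 20/11.25 = 1.78, too low.
- The direction turns when usual care misses 1 − 11.25/12 = 6.25%.

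**The case against.** **Contact is already scheduled.** Psychometric scales, a knowledge test and an experience questionnaire cannot come from chart review, so low-risk subjects must be contacted anyway, and readmission is listed as follow-up data without restriction to Temple. This stands in part. It shows that the gap may be a single call item and that the protocol does not forbid asking. It does not show that the question is put, because the only text that governs it makes it conditional. Appendix Item 3a is not in the text at hand, so whether it asks about care elsewhere could not be checked.

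**The coding is inferred.** This stands. The protocol does not say how readmission status is recorded for a subject with only a Temple ED visit. Non-event is the likely default, not a stated one.

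**The size is wholly assumed.** This stands. If both shares were 20%, 180 × 0.20 × 0.20 = 7.2 readmissions (4.0 points) would be missed, so the figures show scale only. Observed/expected is also this review's measure; the protocol names no calibration measure for Aim 2. Section 8(h) describes the study as a pilot not powered for outcome differences.

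**Stronger readings.** A reader might infer that the rule makes the DERRI appear to separate risk groups better than it does. The protocol does not support this. The low-risk group is the only one with a stated step to find outside visits, so usual care may miss more, and the contrast can move either way. A reader might also infer bias in the treatment comparison. The rule applies only to the observational low-risk group, so the randomised comparison is untouched. The yes/no composite is also unaffected, since a subject with a Temple ED visit already counts there.

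**Conclusion.** The point holds as a minor one. The stated contact rule lets a Temple ED visit replace the question about readmission elsewhere, although Aim 2 concerns readmission. Taken alone, it can only lower the observed low-risk 30-day readmission rate, and it can lower low-risk ED visit counts. The direction follows from the rule together with the likely, but unstated, coding of unasked subjects as not readmitted. The limit to this rule alone matters: dropping unreachable subjects with no Temple visit could raise the observed rate, but that is a separate mechanism.

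The loss is probably small, about 0.75 points at the midpoints of the assumed ranges. That lies well inside the sampling half-width of about 4.7 points, but the error is systematic. How far it occurs in practice depends on whether the implied contacts include the question, which the text at hand does not settle.

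**What to change.** 1. In section 8(f), Low-risk group, ask every subject at about 5 weeks about hospital and ED visits at other institutions, with dates, whatever the Temple record shows. At minimum, ask everyone without a Temple readmission.
2. Put the same question in the 5-week call under Phase A, Data collection, so that ascertainment is the same in all three groups.
3. If a subject with only a Temple ED visit cannot be reached, record readmission elsewhere as unknown, not as none.

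The cost is one question in a contact that the questionnaire and Table 2 already imply. On the assumptions used here it newly reaches 180 × 0.05 = 9 to 180 × 0.15 = 27 subjects with only a Temple ED visit. If ED counts are to be complete, it also reaches those with a Temple readmission, at most about 21 (21.6 − 0.45 = 21.15 at the assumed 12%).

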3) A1c-based adjustment of diabetes therapy: Upon hospital discharge, diabetes therapy will be determined by the PI or co-Investigator (Endocrinologists) based on an algorithm tested in patients with type 2 diabetes,[9] and the American Diabetes Association Standards of Medical Care guidelines as follows [54]:

a) For A1c <7%, resume the pre-admission treatment regimen.

b) For A1c 7-7.9%

- Patients who did not take insulin before admission, discharge on optimized pre-admission treatment regimen (see definition below) or add a non-insulin agent if the prior regimen was already optimal.
- Patients who took basal insulin but not prandial insulin before admission, increase the home daily dose of basal insulin by 10-15% in addition to any non-insulin pre-admission treatments. Non-insulin pre-admission treatments should be optimized.
- Patients who took multiple daily insulin injections (MDI) before admission, increase the home total daily dose of insulin by 10-15% in addition to any non-insulin pre-admission treatments. Non-insulin pre-admission treatments should be optimized.

b) For A1c 8-9%

- Patients who did not take insulin before admission, discharge on 50% of the last inpatient insulin glargine daily dose or 0.2 units/kg in addition to the pre-admission treatment regimen, which should be optimized.
- Patients who took basal insulin but not prandial insulin before admission, discharge on 50-80% of the last inpatient insulin glargine daily dose or increase the home daily dose of basal insulin by 10-15% and/or add rapid-acting insulin before the largest meal at 50-80% of the last inpatient dose or 0.1 units/kg in addition to any non-insulin pre-admission treatments. Non-insulin pre-admission treatments should be optimized.
- Patients who took multiple daily insulin injections (MDI) before admission, discharge on 50-80% of the last inpatient total daily insulin dose or increase the home total daily dose of insulin by 10-15% in addition to any non-insulin pre-admission treatments. Non-insulin pre-admission treatments should be optimized.

c) For A1c >9%

- Patients who did not take insulin before admission, discharge on 80-100% of the last inpatient insulin glargine daily dose or 0.3 units/kg in

Readmission Pilot Trial

addition to the pre-admission treatment regimen, which should be optimized.

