4) Post-discharge support: At 24 to 48 hours post-discharge, a nurse Navigator will call the patient to assess the patient’s status, confirm receipt of and compliance with medications, verify the follow-up appointment schedule, assess for barriers to following the discharge plan, determine the need for a community health worker (CHW) referral, and review blood glucose control (patients who are discharged on non-insulin regimens will be expected to test their blood glucoses at least once a day, and patients who are discharged on an insulin regimen will be expected to test their blood glucoses at least twice a day). Similar phone calls will be made weekly for four weeks following discharge by a Navigator. If a patient reports significant high or low blood glucose levels, then the PI or a co-Investigator (Endocrinologists) will call the patient to adjust diabetes therapy (See Tables 1a and 1b for insulin dose adjustment protocols). Eligible patients will receive a referral for a nursing visit from a local home care agency to assess medical needs for support at home and medication reconciliation. Referral to a CHW may be made if subjects are found to have non-medical needs and/or obstacles to maintaining self-care and attending follow-up appointments. Such non-medical support might include transportation to and from medical appointments, food, housing, or legal assistance, relief from utility bills, verification of insurance, support groups and delivery of durable medical equipment.

Table 1a. **Outpatient basal insulin dose adjustment:**

Basal Insulin	
If mean FBG > 180 mg/dL for the last 2 consecutive days and no episodes of hypoglycemia	Increase daily basal dose by 4 IU
If mean FBG > 140 mg/dL for the last 2 consecutive days and no episodes of hypoglycemia	Increase daily basal dose by 2 IU
If mean FBG between 100 to 140 mg/dL for the last 2 consecutive days and no episodes of hypoglycemia	No Change
If any FBG between 70 – 99 mg/dl	Decrease by 4 IU or 10% of total daily basal dose
If any FBG < 70 mg/dl	Decrease by 8 IU or 20% of total daily basal dose
If any FBG < 40 mg/dl	Decrease total daily basal dose by 30%

FBG=Fasting blood glucose; Hypoglycemia=typical symptoms (e.g., sweating, tremor, acute hunger, anxiety) and/or blood glucose <70 mg/dL

Table 1b. **Outpatient prandial/pre-meal insulin dose adjustment based on subsequent mealtime/HS BG values:**

Pre-meal Rapid Insulin		
Pre-meal Dose, U	BG 70 – 100 mg/dl*	BG 141-180 mg/dl**

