≤ 10 U	Decrease by 1 U	Increase by 1 U
>11- 19 U	Decrease by 2 U	Increase by 2 U
≥ 20 U	Decrease by 3 U	Increase by 3 U
Pre-meal Dose, U	BG 40-70 mg/dl x 1	BG 180-240 mg/dl x 1

Readmission Pilot Trial

≤ 10 U	Decrease by 2 U	Increase by 2 U
>11- 19 U	Decrease by 3 U	Increase by 3 U
≥ 20 U	Decrease by 4 U	Increase by 4 U
Pre-meal Dose, U	BG < 40 mg/dl x 1***	BG > 240 mg/dl x 1
≤ 10 U	Decrease by 4 U	Increase by 3 U
>11- 19 U	Decrease by 6 U	Increase by 4 U
≥ 20 U	Decrease by 8 U	Increase by 5 U

Pre-meal insulin dose adjustment is based on the subsequent BG value, e.g., pre-breakfast insulin dose is based on the pre-lunch BG.

* If > ½ of the mealtime/HS BG values for the week were below target.

**If > ½ of the mealtime/HS BG values for the week were above target.

*** Decrease by 30-40% in the event of severe hypoglycemia (mealtime/HS BG < 40 mg/dl).

BG=blood glucose; Mealtime/HS=pre-lunch, pre-dinner, or bedtime

The above algorithm provides recommended insulin doses and may be modified based on clinical judgment of the investigator or co-investigator.

Usual care: Most aspects of the intervention go above-and-beyond usual care. Patients in the usual care group will receive the standard discharge instructions and medication reconciliation process. Those who are new to diabetes receive training by a floor nurse on using a glucometer as well as a stock set of printed educational materials. The floor nurses also train patients who are new to insulin injections as needed. Patients with diabetes are referred to outpatient diabetes education at Temple on a case-by-case basis as determined by the primary hospital provider team. Diabetes therapy upon discharge is decided on a case-by-case basis by the primary team. Discharge instructions are routinely sent to the primary care physician either by fax or EPIC. Most TUH patients receive a phone call 2 to 4 days after discharge from a CHW that includes checking on the status

Table 2. Timeline for assessments of subjects

Visit #	1	2	3	4	5	6	7	8
Time (weeks)	0	2 days	1	2	3	4	5	13
Intervention group								
Phone call/clinic visit								X
Psychometric assessments	X							X
Diabetes knowledge	X							X
30d endpoints								X
Interview							X	
A1C	X							X
Navigator call		X	X	X	X	X		
Blood glucose		X	X	X	X	X	X	
Adverse events		X	X	X	X	X	X	
Usual care group								
Phone call								X
Psychometric assessments	X							X
Diabetes knowledge	X							X
30d endpoints								X
A1C	X							X
Blood glucose								X

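### Table 1a gives two reduction rows in units or percent without saying which governs; in units, below 26.7 IU a fasting glucose under 70 brings a larger basal cut than the row for under 40

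*Protocol*

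**What the plan says.** Protocol section 8 f), intervention component 4 (post-discharge support), refers to Tables 1a and 1b for insulin adjustment after discharge. Table 1a has three reduction rows for fasting blood glucose (FBG):

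- any FBG 70-99 mg/dL: "Decrease by 4 IU or 10% of total daily basal dose"
- any FBG under 70 mg/dL: "Decrease by 8 IU or 20% of total daily basal dose"
- any FBG under 40 mg/dL: "Decrease total daily basal dose by 30" percent, with no unit alternative

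Nothing in the table or around it says whether the larger amount, the smaller amount or the clinician's choice applies where two are given.

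Component 3 (A1c-based adjustment at discharge) produces some of the basal doses on which the table acts. For patients who took no insulin before admission, the A1c 8-9% tier reads "discharge on 50% of the last inpatient insulin glargine daily dose or 0.2 units/kg" and the A1c >9% tier reads "discharge on 80-100% of the last inpatient insulin glargine daily dose or 0.3 units/kg".

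Two further statements bear on how the table is used. When glucose is significantly high or low, "the PI or a co-Investigator (Endocrinologists) will call the patient to adjust diabetes therapy". After Table 1b the protocol adds: "The above algorithm provides recommended insulin doses and may be modified based on clinical judgment of the investigator or co-investigator".

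**The concern.** A reduction table keyed to falling glucose is expected to be graded, with a lower reading bringing at least as large a cut. The protocol shows that intention twice. Table 1a's percentages rise 10, 20, 30. In the unit columns of Table 1b, the cut for under 40 mg/dL is the largest in every dose band: 4, 6 and 8 U, against 2, 3 and 4 U for 40-70 and 1, 2 and 3 U for 70-100.

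Table 1a mixes a fixed amount with a percentage in two rows and uses a percentage alone in the third. Such rows cannot stay in order at every dose. At low basal doses one of the printed options gives a larger cut for the milder reading. At most doses, two subjects with the same dose and reading can also receive different cuts, both consistent with the table. The table deals with hypoglycemia, so its recommendation should be readable in only one way.

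**Working it through.** The table states no derived figure to reproduce, so the check is algebra on its rows. Let D be the total daily basal dose in IU.

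**Inputs.** From Table 1a: 4 IU or 0.10·D (70-99), 8 IU or 0.20·D (under 70), 0.30·D (under 40). From component 3: weight-based starts of 0.2 and 0.3 units/kg.

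**Where the two forms agree.** 4 = 0.10·D gives D = 40, and 8 = 0.20·D gives D = 40. Below 40 IU the fixed amount is the larger cut; above it the percentage is (at 60 IU, 8 IU against 12 IU).

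**Where the order reverses in fixed units.**
- Row for under 70 against row for under 40: 8 > 0.30·D when D < 8/0.30 = 26.7 IU.
- Row for 70-99 against row for under 40: 4 > 0.30·D when D < 4/0.30 = 13.3 IU.
- If forms are mixed, the 4 IU cut for 70-99 exceeds the 20% cut for under 70 when D < 4/0.20 = 20 IU.

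**In percentages.** 0.10·D < 0.20·D < 0.30·D at every dose, so there is no reversal.

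| Basal dose (IU) | Cut, FBG 70-99 | Cut, FBG under 70 | Ratio of the two forms (40/D) | Cut, FBG under 40 |
|---|---|---|---|---|
| 12 | 4 or 1.2 | 8 (67%) or 2.4 | 3.3 | 3.6 |
| 16 | 4 or 1.6 | 8 (50%) or 3.2 | 2.5 | 4.8 |
| 20 | 4 or 2.0 | 8 (40%) or 4.0 | 2.0 | 6.0 |
| 24 | 4 or 2.4 | 8 (33%) or 4.8 | 1.7 | 7.2 |
| 27 | 4 or 2.7 | 8 (30%) or 5.4 | 1.5 | 8.1 |
| 40 | 4 or 4.0 | 8 (20%) or 8.0 | 1.0 | 12.0 |

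**Overlap of rows.** The row for under 70 has no lower limit, so a reading under 40 satisfies both rows. The table does not say that the row for under 40 takes over.

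**Does the protocol produce doses in this range?** The crossover weight is 26.67 divided by the units per kg:
- 0.2 units/kg: 26.67/0.2 = 133 kg
- 0.3 units/kg: 26.67/0.3 = 88.9 kg

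For example, weights of 60-100 kg give 12-20 IU at 0.2 units/kg and 18-30 IU at 0.3 units/kg.

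**How many starts fall below 26.7 IU?** The protocol gives no body weights, so this is a range under assumptions only. With normally distributed weight, mean 80-110 kg and SD 20-25 kg, the share is 82.5% to 99.6% at 0.2 units/kg and 14.6% to 67.2% at 0.3 units/kg. If the two tiers were equally common, a further assumption, it is 51.2% to 83.4%.

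**The case against.** The strongest reply is that the table does not run by itself. An endocrinologist makes the call, the doses are labelled as recommendations, and clinical judgment may override them. Part of any variation between subjects is therefore discretion that the protocol states openly. This stands, and it limits the practical consequence. It does not remove the inconsistency: permission to depart from a recommendation does not tell the reader what the recommendation is.

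A second reply is that the reversal needs someone to choose 8 IU at a low dose when 20% is printed beside it, and that a reading under 40 also meets the row for under 70. Both points are correct. A reader might infer that the table forces a smaller cut for a severe low than for a mild one. It does not; it permits that result. But the overlap is a second ambiguity, not a cure for the first.

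A reader might also infer that most new insulin starts fall in the affected range. The documents do not support that. Weights and the mix of A1c tiers are not given. Weight-based dosing is one alternative to a percentage of the inpatient glargine dose, and these starts apply only to patients not on insulin before admission. Doses may also have been titrated by the time a low reading occurs.

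Finally, it is tempting to say that the defect causes rebound hyperglycemia or makes the intervention irreproducible for a later trial. Nothing in the protocol shows either. Table 1a is one element of one of four intervention components, and no endpoint or analysis is shown to change.

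**Conclusion.** The inconsistency is real and rests on the table's own figures. The unit and percentage forms agree only at 40 IU/day and no rule selects between them. In fixed units the cut for FBG under 70 exceeds the cut for FBG under 40 below 26.7 IU, and the cut for 70-99 exceeds it below 13.3 IU. The row for under 70 overlaps the row for under 40. For a reading under 70, the two printed forms differ by a factor of 2 to 3.3 at doses of 12-20 IU.

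These thresholds need no outside assumption. The protocol's weight-based starts can fall in the affected range, under 133 kg at 0.2 units/kg and under 89 kg at 0.3 units/kg. How many subjects that means cannot be read from the documents. Application by endocrinologists keeps this from being a critical fault. It should still be corrected, because the table concerns response to hypoglycemia and the correction is cheap.

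**What to change.** The investigators should reconcile the three reduction rows of Table 1a. They should state which form governs in each row where two are printed, and which row governs a reading under 40 mg/dL. They should then check the revised rows across the basal doses that the discharge algorithm can produce, to confirm that the intended order holds throughout. The amounts, and the choice between units and percentages, are for the study endocrinologists to decide. The clinical-judgment clause can stay as it is.

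The cost is a one-table protocol amendment, with no added procedures, visits or patients.

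### The insulin adjustment tables give two different instructions for the same reading (Table 1b, BG < 40; Table 1a, FBG 70-99), and Table 1b has no row for 11 U

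*Protocol*

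**What the plan says.** Both tables belong to component 4 of the intervention (post-discharge support) in Protocol section 8 f). They come into use as follows: "If a patient reports significant high or low blood glucose levels, then the PI or a co-Investigator (Endocrinologists) will call the patient" to change therapy. Readings are reviewed at a call 24 to 48 hours after discharge and then regularly: "Similar phone calls will be made weekly for four weeks following discharge by a Navigator".

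**Table 1b (pre-meal insulin).** For one glucose value below 40 mg/dl, the rows give a decrease of 4 U for doses up to 10 U, 6 U for the middle band, and for doses of 20 U or more "Decrease by 8 U". That column carries footnote ***, which reads "Decrease by 30-40% in the event of severe hypoglycemia (mealtime/HS BG < 40 mg/dl"). The dose bands, repeated in all three blocks of the table, are up to and including 10 U, strictly above 11 U to 19 U, and 20 U or more.

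**Table 1a (basal insulin).** The +2 IU row applies "If mean FBG > 140 mg/dL for the last 2 consecutive days and no episodes of hypoglycemia". The no-change row applies "If mean FBG between 100 to 140 mg/dL for the last 2 consecutive days and no episodes of hypoglycemia". A decrease of 4 IU or 10% applies "If any FBG between 70 – 99 mg/dl". The note under the table defines the blocking event: "Hypoglycemia=typical symptoms (e.g., sweating, tremor, acute hunger, anxiety) and/or blood glucose <70 mg/dL".

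A closing clause says that the doses are recommendations and that the investigators may modify them on clinical judgment.

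**The concern.** 1. **Table 1b, BG < 40.** The footnote could have described a separate, graver event. It does not, because it defines severe hypoglycemia by the same glucose limit that heads the column. One reading therefore carries two written instructions, and nothing says whether the footnote replaces, bounds or adds to the rows.
2. **Table 1a.** The mean-based rows are blocked only by symptoms or a value below 70 mg/dL. A symptom-free fasting value of 70-99 does not block them, yet it triggers a decrease by itself. One glucose record can then meet two rows with different actions, even opposite ones. The any-value row also states no time window.
3. **Table 1b, 11 U.** No band contains this dose. This is a gap, not a contradiction.

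Points 1 and 2 concern low or low-normal readings. Section 9 names hypoglycemia as the risk of A1c-based adjustment of therapy. Section 8 j) relies on weekly calls and on referral for adjustment as the protection after discharge. These tables are the written guide for that adjustment. The pilot is also meant to refine the procedures for a definitive trial, so an ambiguous algorithm could be carried forward.

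**Working it through.** The protocol gives no calculation here, so the check compares the written instructions with each other.

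**Table 1b, BG < 40.** For a pre-meal dose d in whole units, the row decrease is r = 4 (d ≤ 10), 6 (12 ≤ d ≤ 19) or 8 (d ≥ 20). The footnote gives the range 0.30d to 0.40d. The two agree when 0.30d ≤ r ≤ 0.40d, that is, when r/0.40 ≤ d ≤ r/0.30:

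- r = 4: 10 ≤ d ≤ 13.3; within its band, only 10 U.
- r = 6: 15 ≤ d ≤ 20; within its band, 15-19 U.
- r = 8: 20 ≤ d ≤ 26.7; within its band, 20-26 U.

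Examples:

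| Dose (U) | Row decrease (U) | Row as % of dose | Footnote range (U) | Row outside the range by (U) |
|---|---|---|---|---|
| 6 | 4 | 66.7 | 1.8-2.4 | 1.6 above |
| 7 | 4 | 57.1 | 2.1-2.8 | 1.2 above |
| 9 | 4 | 44.4 | 2.7-3.6 | 0.4 above |
| 10 | 4 | 40.0 | 3.0-4.0 | inside |
| 12 | 6 | 50.0 | 3.6-4.8 | 1.2 above |
| 14 | 6 | 42.9 | 4.2-5.6 | 0.4 above |
| 15 | 6 | 40.0 | 4.5-6.0 | inside |
| 26 | 8 | 30.8 | 7.8-10.4 | inside |
| 27 | 8 | 29.6 | 8.1-10.8 | 0.1 below |
| 30 | 8 | 26.7 | 9.0-12.0 | 1.0 below |
| 40 | 8 | 20.0 | 12.0-16.0 | 4.0 below |

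The row lies at least 1 U outside the range at 7 U or less (computed from 4 U), at 12 U, and from 30 U up. At 8-9, 13-14 and 27-29 U it is outside by less than 1 U. At 9, 14, 27 and 28 U the difference is 0.4 U or less, which rounding could explain.

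**Table 1a.** The fasting values below are illustrative. None is under 70 mg/dL and no symptoms are assumed, so the mean-based rows are not blocked.

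- 90 and 130: mean (90 + 130)/2 = 110. This meets the no-change row and, through the 90, the decrease row.
- 85 and 200: mean (85 + 200)/2 = 142.5. This meets the +2 IU row and, through the 85, the decrease row.
- 90 earlier in the week, then 150 and 160: mean of the last two days (150 + 160)/2 = 155. This meets the +2 IU row. It also meets the decrease row if the any-value condition is read over the week between calls. That window is an assumption, since the table states none.

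**Table 1b, coverage.** A dose of 11 U is above the first band, is not strictly above 11, and is below 20. It has no row in any of the three blocks, each with two glucose columns.

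**The case against.** - **Discretion and safeguards.** Endocrinologists make the changes, the doses are recommendations, and a Data Safety Officer reviews adverse events every 3 months. This limits the practical effect. It does not settle the text: freedom to depart from a recommendation does not say which of two written instructions is the recommendation.
- **The footnote may be an alternative way of stating the cut.** Table 1a pairs fixed and percentage decreases in this way, but there the alternative is written out. Table 1b does not write it, and the two forms differ in both directions across the dose range, so neither summarises the other. It stands that they agree at 10 and 15-26 U and nearly agree at several other doses.
- **A low single value is plainly meant to override a mean.** This is a reasonable reading, and the word any may be intended to do it. In the nested rows of Table 1a (> 180 within > 140, < 40 within < 70), a reader can take the more extreme row. That logic does not settle a mean-based row against an any-value row, and the table states no order.
- **The examples are selective.** Values of 90 and 130 may never count as significant and so may never bring the tables into use. The term is undefined. The pair 85 and 200 needs a difference of 115 mg/dL between two fasting readings, and the protocol gives no basis for how often that occurs. Both remarks stand. The examples show that the overlap exists, not how frequent it is.
- **The 11 U gap is typographical.** Very likely. A misread sign in the copy reviewed cannot be excluded either, although the neighbouring signs came through. Points 1 and 2 do not depend on it.
- **Section 9 concerns component 3, not these tables.** This is correct as to its wording. Section 8 j) covers hypoglycemia found during follow-up more generally and carries the argument.

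**Conclusion.** The concern holds. For BG < 40 mg/dl, the Table 1b rows and footnote *** cannot both be followed for whole-unit doses below 10 U, at 12-14 U, or from 27 U up. The difference is at least 1 U at 7 U or less, at 12 U, and from 30 U up, reaching 4 U at 40 U. Table 1a lets one record meet a mean-based row and the 70-99 decrease row without stating precedence or a window. The 11 U gap is minor.

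The calculation assumes whole-unit doses. The protocol gives no distribution of doses or readings, so none of these figures is a rate of affected adjustments. At most the insulin-treated part of the 60 intervention subjects is concerned. No effect on the endpoints, the analysis or the sample size is claimed. The text should be corrected because it bears on patient safety and the correction is cheap. Which instruction is right is a clinical question, and this review takes no view on it.

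**What to change.** The investigators should:

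1. reconcile the BG < 40 rows of Table 1b with footnote ***, so that one reading leads to one recommended action, or state how the two relate;
2. state in Table 1a which row takes precedence when a mean-based row and the any-value 70-99 row both apply, and over what period the any-value row is read;
3. correct the middle dose band of Table 1b so that 11 U has a row.

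The discretion clause can stay. The cost is a wording correction to two tables by protocol amendment, with no change to data collection, endpoints or sample size. The content of the reconciled rules is for the investigators to decide.
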